Traditional healers face a risk of acquiring bloodborne pathogens from contaminated blood and body fluids. While most exposures for unbroken skin do not result in infection, risk of infection varies by the pathogen involved, the type of exposure, the amount of blood involved, and the amount of virus in the patient’s blood at the time of exposure.³⁰ The average risk of HIV infection after a needlestick or cut exposure to HIV-infected blood is 0.3%, and after exposure to eye, nose, or mouth is estimated to be 0.1%.³⁰ “Injections” result in substantial blood exposure- approximately 2 mL of blood per injection, which is in contact with a healer’s bare skin (primarily hands and arms- we find blood under healer fingernails after treatments- but as people touch their faces 23 times per hour, exposure to the mucus membranes is possible).³¹ Healers are often subsistence farmers (resulting in small cuts and abrasions on their hands from planting and harvesting, as well as from regular household activities, including preparing food and washing clothes). Furthermore, they have limiting access to potable water in their homes (thus, limited hand washing opportunities post-“injection”) exacerbating their risk of acquisition. In the Agincourt area (Figure 1), healers have an overall HIV prevalence of 30% (CI: 23%-37%) vs. 19% in the general population;³² in our previous study, healers who reported exposure to patient blood had 2.4-fold higher risk of being HIV-positive than those with no reported blood exposure (59% vs. 25%, respectively).²⁷

Low rates of PPE training and use can place healers at risk. PPE is defined as equipment or instruments (gloves, safety glasses, facemasks, respirators, etc.³³) worn to avoid and/or minimize exposure to hazards that could cause injuries or the spread of infection and illness. Use of PPE has been shown to be effective in reducing occupational exposures.³³⁻³⁵ Healers living with HIV may be perpetuating the epidemic, given their high HIV prevalence and their reluctance to attend clinical services (including HIV counseling, testing, and treatment). Healers may represent a reservoir of HIV-infected individuals with limited health facility contact. After acquiring HIV through their injection practices or elsewhere, healers are at risk of spreading the virus not only to their partners and children but also to other patients through further blood exposure, thus amplifying the effect of limited PPE/poor occupational hygiene.

2. Objectives

The objective of this proposal is to adapt PPE training guidelines issued by the World Health Organization (WHO)³⁶ and the U.S. Occupational Safety and Health Administration (OSHA)³³ for use by healers and to fill the current evidence-to-practice gap by comparing effectiveness of two practical strategies for implementing evidence-based PPE guidelines.

Our proposal compares two implementation strategies to increase PPE use and proper disposal during procedures and decrease the number of risky injections performed (de-implementation of traditional injections): (1) Health care worker (HCW)-led education on blood exposure risk and PPE use through a week-long training, followed by three educational outreach visits at the healer's place of practice vs. (2) "Early adopter" healer³⁷⁻⁴⁰ and HCW co-led training followed by three educational outreach visits. We hypothesize that "early adopter" healer messaging and delivery will have greater impact given their membership within the healer community.

Aim 1. Gather information about how healers and health care workers are learning about PPE use to develop an acceptable and appropriate PPE training program.

Aim 2: Compare fidelity to delivery of PPE training between the HCW-only and the healer plus HCW teams.

We will compare training fidelity of the two teams via three constructs: (1) content, (2) coverage, and (3) duration^{41,42} to determine if there is a difference in fidelity between the two types of teams.

Hypothesis 1: Training fidelity will be greater among healer + HCW teams, as they will have greater motivation to comprehensively deliver education and skill building sessions to healers.

Aim 3: Compare the effects of the two implementation strategies on healer exposure to patient blood.

We will enroll traditional healers into each PPE strategy using a stratified random sampling. Healers will use containers to collect all used sharps and used gloves over a six-month period and complete a low literacy data collection form to document glove use to identify gaps in PPE use.

Hypothesis 1: Healers who are trained by the healer + HCW team will have a higher proportion of glove use during injections than those in the HCW-only trainer arm.

4. Study Population

Population

Traditional healers and biomedical practitioners (including clinicians and nurses) providing patient care in the Bushbuckridge area.

Inclusion Criteria

1. Traditional healers \geq 18 years of age, who are registered as traditional healers with the government of South Africa, are currently practicing in the Bushbuckridge area, and conduct traditional vaccinations.

2. Biomedical practitioners \geq 18 years of age, who are currently providing health care services to patients at government or private health facilities in Bushbuckridge.

3. Community members \geq 18 years of age, who currently live in Bushbuckridge and sought health care services from a traditional healer in the past year.

Exclusion Criteria

1. Traditional healers <18 years of age, who are not registered as traditional healers with the government of South Africa, are not currently practicing, or do not conduct traditional vaccinations on their patients.
2. Biomedical practitioners < 18 years of age or who are not currently providing health services in the Bushbuckridge area.
3. Community members < 18 years of age or who do not seek health care services from traditional healers.

Calculation of Sample Size & Sampling Strategy

Aim 1: We anticipate recruiting 20 traditional healers and 10 health care workers to achieve data saturation.

Aim 2: With $n=61$ traditional healers per arm, we will have approximately 80% power to detect a difference between intervention arms for the fidelity scores of 0.5 standard deviations, and approximately 90% power to detect a difference of 0.6 standard deviations. These power calculations are based on a two-sample t-test and are likely conservative because the primary analyses will incorporate multiple (correlated) observations per healer. It should be noted that we do not have preliminary data for the fidelity scores; therefore, our power calculations are based on generic standard deviations. Finally, it should be noted that the sample size was primarily based on ensuring adequate power for Aim 3.

Aim 3: From preliminary data collected from healers in Agincourt in 2019, the median proportion of glove use during vaccinations was 0.44, mean 0.39, and standard deviation (SD) 0.39. Our sample size is calculated based on a two-sample t-test and incorporates these preliminary data. Assuming the SD=0.39, then we anticipate needing 61 healers per arm (total of 122) to have 80% power to detect at the ($\alpha=0.05$ -level) a difference of 0.2 in the proportion glove use between the HCW-only and the healer + HCW teams (e.g., 0.4 vs. 0.2). Included below is the variability in power given different deltas (differences in the mean proportion of blood exposure between the two arms) (Table 1). Note, that these power calculations are approximate as primary analyses will be performed using negative binomial regression. Power calculations using negative binomial regression would require assuming a distribution of the offset (number of procedures performed per healer), which substantially complicate the calculations. Therefore, we present power calculations based on two-sample t-tests, which should be fairly similar.

Table 1 Sample Size and Power

N	Δ	SD	α	P
61	0.17	0.39	0.05	66.57
61	0.18	0.39	0.05	71.52
61	0.19	0.39	0.05	76.08
61	0.20	0.39	0.05	80.22
61	0.21	0.39	0.05	83.89

61	0.22	0.39	0.05	87.08
61	0.23	0.39	0.05	89.81
61	0.24	0.39	0.05	92.09
61	0.25	0.39	0.05	93.96

N: number of healers per arm

Δ: Difference to detect (delta)

SD: Standard deviation

α: Significance level (alpha)

P: Power, %

Randomization strategy

To avoid concerns that, despite randomization, one intervention arm of healers will substantially differ from the other, we will conduct stratified randomization. Specifically, we will stratify based on healer sex and the number of patients seen in a given month (dichotomized into high/low based on the estimated median number of patients seen in the past month). This will result in 4 strata. At the time of randomization, each healer will be put in a strata and equal numbers of healers in each strata will be randomized to the two intervention arms.

5. Methods

Measurement of Results

Aim 1: We will use qualitative measures to understand the best strategies to delivery PPE training to traditional healers in Bushbuckridge.

Aim 2: We will rate training fidelity via two constructs: (1) content and (2) coverage^{41,42} during the week-long training session and community-based outreach sessions (Appendix 2). Understanding the fidelity of training delivery is essential to interpreting the effect of the intervention on PPE behavior change. If HCW + healer teams can deliver training with greater or equal fidelity than HCWs alone, PPE training can be more quickly scaled up nationwide (given the large number of healers) and conducted at lower cost (healers charge considerably less per hour than HCWs). We believe that the healer + HCW teams may have more motivation to deliver the program with fidelity during community-based sessions than the team of HCWs alone because of healers' desire to protect their peers living in their own community. Three HCWs who volunteer to work on this project will be randomly assigned to the intervention team (along with the healers), with six volunteer HCWs assigned to the control arm.

Aim 3: Healers will complete an interviewer-assisted survey immediately post training (Appendix 3) using the Consolidated Framework for Implementation Research framework⁴³ (compatibility of PPE with current behavior, peer pressure to use PPE, perception of the inclusiveness of the training process, cost) and individual characteristics from the situated-IMB model (Figure 3)^{44,45}. During the six months of the trial, healers in each arm will record data on our primary outcome: the proportion of injections conducted using PPE in two ways.

(1) Collect used sharps and PPE. Healers will be given containers to place all used gloves and razors/sharps to both ensure healer safety and allow us to count materials used (healers use gloves and a single razor once per patient and subsequently throw them into latrines or trash piles). We will use the *number of glove pairs as the numerator* (number of times they used gloves during procedures) and the *number of razor blades as the denominator* (number of injections given). While some may be concerned with social desirability bias, healers have been told for years to use gloves and were very open with us about their non-use. Healers have no reason to

under- or over-inflate their PPE use as it will not benefit them- in fact, they would have to buy the razor blades or travel to a health facility to obtain additional latex gloves, something that seems unlikely in this population. (2) Self-report. Healers will record behavior (injection and glove use) every time they conduct an injection.

Study Procedures

Aim 1:

Phase 1: Information Gathering: We will interview select traditional healers and health care workers who have received some training on the use and disposal of PPE. Among traditional healers we will probe into how we can improve the training they receive, their preferred method of receiving information, and perceived gaps in their knowledge. From health care workers, we will gather information about how they were trained in the donning and doffing of PPE, aspects of the training that they believe would be most useful to traditional healers, and strategies to deliver these messages in a way that would be accessible to those with low levels of literacy.

Phase 2: Production of Draft Program: After we gather information from healers and health care workers, we will produce a draft of our training program. Our team will ensure we are maintaining fidelity to core elements and the underlying theoretical framework of the original evidence-based intervention. If there are substantive changes, we will draft additional measures to assess impact of these changes on the intervention outcomes. We will also develop quality assurance metrics (e.g. to ensure healers are using and disposing of PPE safely) and process measures to track the program's success.

Phase 3: Topical Experts: With our advisory counselor, as well as local leaders (e.g. leader of the traditional healer association, head of HIV care and treatment in the Department of Health), we will elicit feedback on our draft protocol. These experts will be tasked to focus on "big picture" issues, specifically sustainability and integration into district, provincial, and national level systems.

Data Collection:

In-depth Interview Question Guide: All participants will provide feedback on the acceptability, feasibility, and appropriateness of PPE training via open-ended questions (e.g. What information was most useful?), as well as questions about perceived barriers and facilitators to PPE training (How difficult will it be to use the sharps containers?) (Appendix 1).

Aims 2 & 3: Traditional healers randomized to both the control and intervention arms will receive PPE education and training, general HIV prevention education and skill building (including condom use, positive prevention, and pre-/post-exposure prophylaxis services), and three educational outreach and coaching visits at the healer's place of practice to provide on-the-ground advice and support for PPE use. These training and educational outreach sessions are designed to allow healers to receive education about bloodborne disease transmission (information), accurately assess their risk of contracting bloodborne illness (motivation), and develop skills to effectively don, doff, and dispose of used PPE (behavior) (Appendices 2 and 3). Outreach visits will focus on delivering five key messages and troubleshoot any issues healers may have in following recommendations. We will assess the impact of our evidence-based PPE intervention on the knowledge, motivation, and behavioral skills developed by traditional healers using the Situated Information Motivation and Behavioral Skills (Situated-IMB) model.⁴⁴ The use of in-class

and educational outreach strategies have yielded improvements in clinical care delivery,⁴⁶⁻⁴⁸ including use of PPE,⁴⁹ among physicians, nurses, and community health workers in low-resource settings. These strategies were selected in consultation with traditional healers in Agincourt who reported never having received training on how to protect themselves from exposures based on the strategies used around the world to train health care providers to avoid infection.^{33,36,49-51} PPE use is feasible and acceptable to most healers and their patients already,²⁷ but they lack the knowledge and/or motivation to use gloves properly and regularly.

Our intervention arm will receive the same training and educational outreach as the control arm, but with training and outreach conducted by a clinical team that includes healers who adopted and use PPE on their own (early adopters).³⁷⁻⁴⁰ Early adopters are people who identify a new behavior as innovative (i.e. use of latex gloves) and adopt this behavior before the majority of their colleagues. Used primarily in the Diffusion of Innovation Theory⁵² to explain adoption of new behaviors, we hypothesize that the strategy of engaging early adopting healers as trainers in collaboration with HCWs will increase peer pressure, perceived tension for change, participant self-efficacy, and acceptability of PPE use among healers who do not use any barrier to blood exposure. Early adopters can achieve this by highlighting relative advantages, compatibility with their role of a traditional healer and leader in the community, simplicity, and ease of trialability of using gloves with patients.⁵²

Participants will receive a baseline and end line (7 months post- training) HIV test (to detect any seroconversion events and to determine if those living with HIV are as motivated to use PPE as those who are HIV-negative). Participants will also complete baseline and end line surveys to assess their knowledge, motivation, and behavioral skills to determine the impact of training on the healer. Once a month, a study assistant will visit each healer to collect all used sharps and PPE; three times during the study the study assistant will also conduct observations of healers using PPE to determine if they are using it correctly post-training.

Healers and healer care workers who are selected, consent and contribute to the training of healers will be reimbursed for their transportation to the training venue and provided with a small token of appreciation (a voucher to a local store for R150) at the conclusion of the workshops.

6. Study Location

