Aim 2: Analysis plan for content: A numeric scale will be used to assess the fidelity of the delivery of *each* topic in the training session. Topics include: (1) Delivered information about the definition of PPE, (2) Provided information about when to use PPE, (3) Provided information about what types of PPE to use in different circumstances, (4) Provided information about the appropriate fit of PPE, (5) Provided do's and don'ts of glove use, (6) Provided information about don PPE, (7) Provided information about how and where to remove PPE, (8) Provided information about how to safely store used PPE, (9) Provided information about hand hygiene, (10) Provided instruction and feedback during PPE practice session. Each of the ten training items will be scored (each with a score of 0-10; 10 represents the greatest fidelity to the training guide, 0 not covering the material at all) for a total of 100 points. The summation of all scores across topics will be used to measure fidelity to content for that training session. Each participant will participate in three training sessions. The mean difference between the two interventions in the total fidelity scores will be estimated using mixed effects linear regression models with 95% confidence intervals (CIs). These models will include random effects for the participant (to account for correlation across multiple sessions) and the trainer (to account for one trainer instructing multiple participants) and a 95% CI will be constructed. The outcome will be transformed as necessary to meet modeling assumptions. Covariates will include patient volume, sex, and baseline age. Any missing data will be imputed using chained equations with 20 imputation replications. Based on prior experience working with healers, we anticipate very low rates of loss to follow-up (LTFU). Healers who are LTFU will be censored at the time of their last recorded data collection, and inverse-probability of censoring weights based on healer characteristics randomization will be used, if necessary, to account for differences between healers who are LTFU and those who remain in the study.

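### The Aim 2 power is called conservative without support: it counts the gain from repeat sessions but leaves out the between-trainer variance that the planned models include

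*Combined protocol and SAP*

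**What the plan says.** Section 4 (Calculation of Sample Size & Sampling Strategy, Aim 2) states: "With $n=61$ traditional healers per arm", the study has "approximately 80% power to detect a difference between intervention arms for the fidelity scores of 0.5 standard deviations"; for 0.6 SD the stated figure is about 90%. On method it says "These power calculations are based on a two-sample t-test", and that the calculations "are likely conservative because the primary analyses will incorporate multiple (correlated) observations per healer". The same paragraph admits that there are no preliminary fidelity data, that the SDs are generic, and that the sample size rests mainly on Aim 3. It gives no number of trainers, trainer ICC or design effect.

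Section 7 (Data Analysis, Aim 2) analyses the content score, from three sessions per healer, in a mixed linear model with random effects for the participant and for "the trainer (to account for one trainer instructing multiple participants"). The coverage model also has trainer random effects.

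Section 5 (Measurement of Results, Aim 2) assigns three HCWs to the intervention team, alongside the healers, "with six volunteer HCWs assigned to the control arm". Section 8 (Recruitment and Consent, Aims 2 and 3) plans to recruit up to 10 healers as trainers.

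**The concern.** Repeated scores on the same healer average out session-to-session noise, and that is the whole basis for calling the t-test conservative. The content score, however, rates what the trainer delivers. If trainers differ, that difference is shared by every healer and session they handle. It enters the arm comparison divided by the number of trainers, so more healers or more sessions do not reduce it. The analysis section recognises this and the power paragraph does not.

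The consequence lies in how a null result would be read. Section 5 treats fidelity as necessary for interpreting the intervention effect and builds a scale-up and cost argument on the healer teams doing at least as well as HCWs alone. A non-significant difference from a study believed to have at least 80% power invites the conclusion that fidelity is equal. The data may be too imprecise to support that.

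**Working it through.** **Inputs from the plan.** 61 healers per arm; 3 sessions per healer; effects of 0.5 and 0.6 SD; HCW trainers 3 (intervention) and 6 (control); up to 10 healer trainers, so 3 to 13 intervention trainers depending on how the unit is coded. Alpha of 0.05 is stated only for Aim 3; two-sided 0.05 is assumed here.

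**Inputs not in the plan, shown as ranges.** Trainer ICC; healer share *s* of the variance (0 to 0.8); whether the SD is that of one session or of a healer's mean.

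**Step 1: the plan's own figures.** Variance of the difference = 2/61 = 0.0328, SE = 0.181. For 0.5 SD, 0.5/0.181 = 2.76, giving power of 78.9% (normal) or 78.2% (t, 120 df). For 0.6 SD the results are 91.2% and 90.8%. The stated figures reproduce to rounding.

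**Step 2: add the trainer term.** With K1 and K2 trainers:

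variance = ICC × (1/K1 + 1/K2) + 2 × [s + (1 − ICC − s)/3]/61

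Setting s = 1 − ICC gives the reading in which the SD is that of a healer's mean and repeats bring no gain (lowest power). Setting s = 0 gives a per-session SD with no healer-level correlation (highest power). The formula assumes independent, equally loaded trainers with the same variance in both arms, each handling all of a healer's sessions.

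Example, 3 versus 6, ICC 0.05, 0.5 SD:
- Low end: 0.05 × 0.5 + 2 × 0.95/61 = 0.0250 + 0.0311 = 0.0561; SE 0.237; ratio 2.11; power 56%.
- High end: 0.0250 + 2 × (0.95/3)/61 = 0.0250 + 0.0104 = 0.0354; SE 0.188; ratio 2.66; power 76%.

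Power for 0.5 SD, low end to high end (df = K1 + K2 − 2):

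| Trainers | ICC | Normal | t |
|---|---|---|---|
| 3 vs 6 | 0.05 | 56–76% | 45–63% (7 df) |
| 3 vs 6 | 0.10 | 43–53% | 34–42% |
| 3 vs 6 | 0.20 | 29–33% | 23–26% |
| 13 vs 6 | 0.05 | 67–91% | 62–88% (17 df) |
| 13 vs 6 | 0.10 | 58–77% | 53–72% |
| 13 vs 6 | 0.20 | 45–55% | 41–50% |

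For 0.6 SD with 3 versus 6 trainers and ICC 0.10, power is 57–69% (normal) or 45–56% (7 df).

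**Step 3: where the two effects balance.** With a per-session SD, setting the variance equal to 2/61 gives

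break-even ICC = (2/61) × (2/3) × (1 − s) / (1/K1 + 1/K2 − 2/183)

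- 3 vs 6: 0.0219 × (1 − s)/0.489, which is 0.045 at s = 0, 0.022 at s = 0.5 and 0.009 at s = 0.8.
- 13 vs 6: 0.0219 × (1 − s)/0.233, which is 0.094, 0.047 and 0.019.

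Below these values the t-test figure is indeed conservative on a normal reference; above them it is optimistic. With 7 df the 3 versus 6 values fall to 0.028 at s = 0 and 0.005 at s = 0.5; at s = 0.8 power is already below the t-test figure at ICC 0.

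**Step 4: can healers compensate?** With 3 versus 6 trainers and ICC 0.10, unlimited healers leave a variance of 0.10 × 0.5 = 0.05, hence power of about 61% (normal) or 49% (7 df) for 0.5 SD.

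**Step 5: precision.** With a healer-mean SD, 3 versus 6 trainers and ICC 0.10, the variance is 0.05 + 2 × 0.90/61 = 0.0795. The 95% interval half-width is 2.365 × 0.282 = 0.67 SD (7 df), against 0.36 SD under the t-test.

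**The case against.** The strongest reply is that no trainer ICC is documented, so nothing shows the stated power to be too high. The argument about multiple observations makes most sense with a per-session SD, and on that reading small ICCs leave the claim intact. With 3 versus 6 trainers and s = 0.5, power on a normal reference is 92%, 86% and 80% at ICC 0, 0.01 and 0.02. The intervention arm also has healer co-trainers, so three trainers is the unfavourable end of the count. Part of the loss under t with 7 df comes from the choice of reference: at ICC 0 with a healer-mean SD, that choice alone takes power from 78% to 66%, and the plan specifies no df method. All of this stands, which is why ranges are shown.

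A reader might therefore infer too much in two ways. One is that the trainer effect definitely makes the stated power optimistic. The documents do not support that, because the sign depends on the ICC, the trainer unit and the SD basis. A sizeable ICC is plausible for a score of trainer behaviour, but that is a judgement. The other is that the t-test figure itself is wrong because it computes to 78.2%. The plan says approximately 80%, so this is rounding.

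It is also fair that the sample size comes from Aim 3 and that the planned models already include the trainer effect. The point is therefore confined to the power statement; it identifies no bias in the analysis.

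**Conclusion.** The claim of conservatism is unsupported. It credits the benefit of repeated sessions and omits a variance component that the plan's own models contain. Whether the net result is optimistic is conditional. With 3 versus 6 trainers, power for 0.5 SD is below the t-test figure at ICC 0.05 and above for every healer share tried. With 13 versus 6 it is below at ICC 0.10 and above, but at 0.05 it can fall on either side. The claim survives only with a per-session SD and a trainer ICC under about 0.01–0.045 (3 versus 6) or 0.02–0.09 (13 versus 6), on a normal reference. These figures rest on assumed ICCs and healer shares, two-sided alpha of 0.05 and balanced trainer loads, and they apply to the content score. Confidence is moderate.

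**What to change.** In section 4, Aim 2, delete the clause that calls the calculations conservative. State what counts as a trainer (HCW, healer co-trainer, or the pair or team delivering a session) and whether the SD is per session or per healer mean. Replace the two power figures with a small table of power, or expected confidence interval width, over trainer ICC 0 to 0.30 and trainer counts from 3 versus 6 through 13 versus 6. Use the step 2 formula, including its session term, and name a small-sample df method, to be used in the analysis as well.

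Aim 2 can keep its directional hypothesis, and enrolment does not change. The cost is a few sentences and one table; the downside is that the stated power will look less favourable.

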Analysis plan for coverage: We will calculate the percentage of sessions completed as the actual number of sessions completed for a participant divided by the total number of planned sessions. The percentage of sessions completed between the two intervention arms will be compared using mixed effects Poisson regression with the number of planned sessions (in most cases 3) as an offset. 95% confidence intervals will be constructed. The models will include random effects for the trainers. Covariates will include patient volume, sex, and baseline age. Missing data and LTFU will be handled as described above.

Aim 3: The analysis will follow intent-to-treat protocol. Our primary outcome is the proportion of a healer's procedures that were conducted using latex gloves (numerator = number of procedures with blood exposure, denominator = number of procedures). We will compare the blood exposure proportions between the two study arms using a negative binomial regression model. In the negative binomial regression, the outcome will be the number of times gloves were used and the number of procedures performed by the healer (number of razor blades) will be included as an offset. Such an analysis is appropriate because it properly accounts for heterogeneity between healers in the number of procedures performed, and the resulting estimates from the model can be interpreted as relative proportions (proportion of procedures with blood exposure in Arm 1 vs. proportion of procedures with blood exposure in Arm 2). In addition to our primary intervention

exposure variable, we will include healer sex and baseline age as covariates in our model. Sensitivity analyses will compare blood exposure proportions between the two intervention arms using a two-sample t-test; a Wilcoxon rank sum test will be fit as needed to avoid normality assumptions.

Based on prior experience working with healers, we anticipate very low rates of loss to follow-up (LTFU). Healers who are LTFU will be censored at the time of their last recorded data collection, and inverse-probability of censoring weights based on healer characteristics randomization will be used, if necessary, to account for differences between healers who are LTFU and those who remain in the study. Missing data will be imputed using chained equations and 20 imputation replications.

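### The 80% power for Aim 3 belongs to a t-test; the primary negative binomial model, with no robust variance named, has about 27–63% under the plan's SD at 10 or more procedures per healer

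*Combined protocol and SAP*

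**What the plan says.** **Sample size** (section 4, Calculation of Sample Size & Sampling Strategy, Aim 3). Pilot data give a mean proportion of glove use of 0.39, median 0.44 and SD 0.39. A t-test at SD 0.39, difference 0.2 and alpha 0.05 leads to 61 healers per arm; Table 1 lists 80.22% power. The section calls the power approximate because the primary analysis is negative binomial. It explains that power for that model would need an assumed distribution of procedures per healer, and concludes: "we present power calculations based on two-sample t-tests, which should be fairly similar". No calculation supports this.

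**Measurement** (section 5, Measurement of Results, Aim 3). Glove pairs are the numerator and razor blades the denominator, because "healers use gloves and a single razor once per patient".

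**Analysis** (section 7, Data Analysis, Aim 3). The model is specified as follows: "In the negative binomial regression, the outcome will be the number of times gloves were used". Each healer's razor-blade count enters as the offset. On covariates, "we will include healer sex and baseline age as covariates in our model". No variance estimator is named. The t-test has a supporting role only: "Sensitivity analyses will compare blood exposure proportions between the two intervention arms using a two-sample t-test".

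**Aim 2 coverage** (same section) uses "mixed effects Poisson regression with the number of planned sessions (in most cases 3) as an offset".

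**The concern.** With one pair of gloves and one razor per patient, the outcome is in essence a number of successes out of a known number of trials. A negative binomial model with a log offset treats it as an unbounded count with variance μ + αμ². An SD of 0.39 on a 0–1 scale means that many healers sit near 0 or near 1. To accommodate the pile near 0, maximum likelihood chooses a large α. That α implies a long upper tail which bounded data cannot have, so the model-based standard error is too big.

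At stake is the power of the primary comparison. The trial could report a null primary result, with an interval that is too wide, for an effect it was sized to find. The t-test beside it might be significant, but a sensitivity analysis does not rescue a negative primary test. Leaving the variance estimator open also means the choice could be made after the data are seen, when it may decide the result.

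**Working it through.** **1. The plan's own figure.** Noncentrality = 0.2 / (0.39 × √(2/61)) = 2.83 on 120 df, two-sided 5%: power 80.22%. Every row of Table 1 reproduces, and the exact t-test needs 61 per arm. The arithmetic is right; the step from t-test to negative binomial is what fails.

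**2. One case by hand: 0.4 vs 0.6, 20 procedures per healer, SD 0.39 in both arms.**
- Actual sampling SD of the log ratio ≈ √[(0.39²/61)(1/0.4² + 1/0.6²)] = √(0.002493 × 9.028) = 0.150. Simulated: 0.148.
- The α that would match the observed variance is 0.39²/p² − 1/(20p), which is 0.83 at p = 0.4 and 0.34 at p = 0.6. The mean α fitted by maximum likelihood was 1.255.
- Model SE = √[2 × 1.255/61 + (1/61)(1/8 + 1/12)] = 0.211. Simulated: 0.210.
- Model-based power = Φ[(ln 1.5 − 1.96 × 0.211)/0.150] = Φ(−0.06) ≈ 48%. Simulated: 48%.
- With a correct SE: Φ[(0.405 − 1.96 × 0.150)/0.150] = Φ(0.74) ≈ 77%.

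**3. Simulations, 61 per arm.** The documents do not give procedures per healer, so volumes are assumed. Healer proportions follow beta distributions.

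Simulation A: lognormal volumes (CV 0.9), 1000 replicates, Monte Carlo SE up to 1.6 points. Model-based power:

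| Mean procedures | 5 | 10 | 30 | 100 |
|---|---|---|---|---|
| 0.4 vs 0.6, 0.39 = SD of recorded proportions | 71% | 63% | 50% | 37% |
| 0.4 vs 0.6, 0.39 = true between-healer SD | 56% | 50% | 43% | 34% |
| 0.4 vs 0.2, recorded SD | 66% | 56% | 41% | 30% |
| 0.4 vs 0.2, true SD | 54% | 50% | 37% | 27% |

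In the same runs the t-test gave 72–82% and sandwich standard errors 68–79%. At 3 procedures (recorded SD), model-based power was 79% and 72%, against 79% and 78% by t-test.

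Simulation B: separately coded, fixed volumes, recorded SD, 600 replicates.

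| Procedures | 10 | 20 | 50 | t-test | Sandwich |
|---|---|---|---|---|---|
| 0.2 vs 0.4 | 52% | 38% | 28% | 79–80% | 74% |
| 0.4 vs 0.6 | 61% | 48% | 41% | 80–83% | 79–82% |

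With varying volumes (mean 10–50) and 0.39 as the true SD, the lowest values were 67% (sandwich) and 70% (t-test).

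**4. Null rejection** (both arms 0.4; mean 10/30/100): 2.6/0.5/0.6% with recorded SD and 1.3/0.6/0.1% with true SD. Sandwich: 3.6–6.5% (5–100 procedures).

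**5. What does and does not change the result.**
- Likelihood-ratio test: within about 3 points of Wald.
- Sex and age in the model: 0.4 vs 0.6 at mean 30, 47% model-based and 78% robust.
- 10% of razors not deposited, so that glove pairs exceed blades for 6–19% of healers: 0.4 vs 0.6 gives 72/63/48/36% at means 5/10/30/100; sandwich 71–79%.
- Lower SD, 0.4 vs 0.6: 61–85% at SD 0.35 (t-test 75–88%); 79–96% at SD 0.30 (t-test 82–96%).
- SD 0.39 in the 0.4 arm and 0.28 in the 0.2 arm: 64–89% (t-test 81–90%).

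**6. Aim 2 coverage (secondary).** For sessions completed out of 3, Poisson overstates the SE by about 1/√(1 − p): 3.2 times at 90% completion and 2.2 times at 80%, if sessions are independent. With within-healer correlation 0.3, divide by √(1 + 2 × 0.3) = 1.26, giving 2.5 and 1.8 times. No stated power depends on this.

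**The case against.** *The range rests on things the plan does not fix.* This is true of procedure volume, and 0.39 is a pilot SD that may not persist after training. At about 3 procedures or at SD 0.30 the problem is minor. But 0.39 is the plan's only SD and the whole basis for 61 per arm, and 10 procedures over six months is fewer than two a month.

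*The beta shape does not match the pilot.* Also true: a beta with mean and SD 0.39 has a median of about 0.24, whereas the pilot median is 0.44. The objection does not help the plan. A mixture matched to the pilot mean, SD and median gave 44/28/9% at means 10/30/100. So 27–63% is an illustration, not a bound. In the plan's 0.4 vs 0.2 example, SD 0.39 is also close to the maximum possible, √(0.2 × 0.8) = 0.40, so those cells are extreme.

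*The analyst might use robust standard errors.* Possibly, particularly if censoring weights are applied. Model-based errors are the default reading, not a stated choice. With sandwich errors the similarity claim is nearly right, which is why naming the estimator matters.

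*The power is labelled approximate, and the error is conservative.* Both are so. A fall from 80% to roughly half or less is still more than approximation, and a missed effect would misinform the larger trial that this study is meant to prepare.

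*Coverage is a separate matter.* It is kept as a secondary remark. The SE factors above ignore the planned trainer random effects.

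**Conclusion.** The concern holds. Table 1 is correct for a t-test, but 80% does not describe the primary test as written. With model-based standard errors, SD 0.39 in both arms, a difference of 0.2 and about 10 to 100 procedures per healer, power is about 27–63% under beta-shaped proportions. It can be lower if many healers never use gloves. Sandwich standard errors restore about 67–82%, close to the t-test. The result rests on assumed volumes, no dropout, and the glove count as the outcome, as the model sentence specifies. Type I error is protected; the loss is in power and precision.

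**What to change.** 1. In section 7, Aim 3, keep the log link and razor-blade offset, so that the estimand remains a relative proportion. State that the primary test and 95% CI use sandwich (robust) standard errors. A quasi- or beta-binomial model is an alternative only if glove pairs cannot exceed razor counts; unreturned razors would break it, whereas the sandwich approach still worked in that check.
2. In section 4, Aim 3, replace the similarity claim with simulated power for the test actually used, over stated ranges of procedures per healer and SD (for example 0.30–0.39). Include a shape consistent with the pilot median.
3. Secondary: analyse Aim 2 coverage as binomial (sessions completed out of planned), or as Poisson with robust standard errors.

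The cost is SAP wording, one line of code and a short simulation, with no new data or participants. The sponsor may have to report power near 70% rather than 80% in some SD 0.39 scenarios.
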